Can Mental Health Chatbots Help Chronic Disease Populations?

[Evaluating the Usefulness of an Artificial Intelligence (A.I.) Mental Health Chatbot in a Healthcare Setting]

Protocol and Statistical Analysis Plan

NCT04620668

October 15, 2020

Updated February 13, 2024 for title page, formatting

People dealing with chronic health conditions are susceptible to mental health issues such as depression and anxiety (Clarke & Currie, 2009). Providing conventional mental health services to all of these individuals is not practical given the limited resources of the healthcare system. Artificial intelligence (A.I.) mental health chatbots may be an accessible and costeffective means by which people can receive some degree of mental health support while they cope with their conditions. These automated programs act as a source of virtual support, talking with individuals and providing them with therapeutic exercises to improve their mental wellbeing. Several chatbots have been designed to deliver interventions based on popular psychological therapies (e.g., Wysa, Woebot, and Tess). Research has shown that these programs can reduce symptoms of depression, anxiety, and stress in nonclinical populations (Fitzpatrick et al., 2017; Fulmer et al., 2018; Inkster et al., 2018; Ly et al., 2017). However, the effectiveness of these programs has not been tested in chronic disease populations.

The purpose of the current research is to gain a better understanding of the usefulness of mental health chatbots for chronic disease populations. This research will be guided by two fundamental objectives: (1) to determine whether a mental health chatbot can reduce or prevent negative mental health symptoms in individuals who are dealing with a chronic health condition, and (2) to learn more about how individuals with a chronic health condition view these programs, particularly in terms of their potential benefits or drawbacks when used in healthcare settings. This research will focus on two specific chronic disease populations that are prone to elevated levels of mental health symptoms: people with arthritis and diabetes.

Method

Design

The study objectives will be pursued using a mixed-method research design (Creswell & Plano Clark, 2011), which will involve collecting and analyzing quantitative data on individuals' mental health symptomology and qualitative data on their experiences with the mental health chatbot.

Sample

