Participants will be individuals between the ages of 19 and 65 who have a diagnosis of diabetes (type 1 or type 2 diabetes) or arthritis (osteoarthritis, rheumatoid arthritis, or another type of arthritis). Although people of any age might be susceptible to mental health issues when dealing with these conditions, individuals in the young adult and middle adult age groups may be at particularly high risk because they have to navigate certain life obligations while coping with their conditions (e.g., caring for a young family, working a job) that many older and younger individuals do not. They are also more likely to use and be familiar with chat-based programs than young children or older adults, meaning that they will almost certainly have the modest technical knowledge required to complete the study.

A power analysis conducted using G*Power (Heinrich-Heine-Universität, Düsseldorf) indicated that a total of 40 participants would be required for the quantitative portion of the study, assuming a moderate effect size, .80 power, an alpha level of .05, and a moderate correlation between repeated measures (.50). However, a larger number of participants (N = 60) will be sought to strengthen the analysis. Individuals will be excluded from participation if they are receiving ongoing treatment from a mental health professional, if they already use a mental health chatbot, or if they started or experienced a dosage change in a psychopharmacological drug within the previous month. Participants will also need to have a phone with an active Internet connection. Participants will be offered a \$20 gift card (Canadian funds) to an online retailer of their choice for completing the study. Participants who drop out of the study prior to

completion will be eligible for a \$5 gift card. An additional \$10 gift card will be offered to participants in the treatment group who complete an optional interview following the main study. **Setting**

The study researchers will be based at the Centre for Research in Integrated Care (CRIC) at the University of New Brunswick in Saint John. The centre will provide access to workspace and necessary equipment and software. All participant communication will occur remotely through phone calls, videoconferencing, and/or email. The developer of the chatbot, Touchkin eServices, will provide technical support and assistance to the research team as necessary from their location Bengaluru (Bangalore), India.

Procedure

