Participants will be recruited through social media channels (including online groups), newspaper advertisements, and emails and newsletters from relevant organizations (e.g., the Arthritis Society, Diabetes Canada). After volunteering to participate, participants will set up a phone or video conferencing call with the primary investigator to orient them into the study. Participants will be randomly assigned to either a treatment group or control group. Those assigned to the treatment group will download the mental health chatbot Wysa (Touchkin eServices, Bangalore) on their smartphones. They will be encouraged to interact with the chatbot at least two times per week over a period of four weeks. Participants assigned to the control group will receive no chatbot (i.e., they will be in a no-treatment control group).

Regardless of their group assignment, participants will complete online materials via Qualtrics at the outset of the study, two weeks into the study, and four weeks into the study (i.e., the final assessment point). At the outset of the study, participants will fill out an informed consent form, a demographic questionnaire, and four psychological assessments tools: measures of depression (Patient Health Questionnaire; Kroenke et al., 2001), anxiety (Generalized Anxiety Disorder Scale; Spitzer et al., 2006), stress (Perceived Stress Scale; Cohen & Williamson, 1988), and life satisfaction (Satisfaction with Life Scale; Diener, et al., 1985). Two weeks into the study, participants will complete the four psychological assessment tools a second time. Four weeks into the study, participants will complete the four assessment tools a final time, and those in the treatment group will be presented with a post-study questionnaire that contains qualitative questions regarding their experiences with the chatbot. Participants in both groups will be presented with a debriefing form providing more information about the study. Those in the control group will be given the opportunity to download and use the chatbot.

To facilitate participant compliance, email reminders about outstanding surveys will be sent throughout the week as necessary. In addition, participants in the treatment group will be sent a general reminder about the intervention once per week.

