After the data from the four-week study are analyzed, a subset of participants from the treatment group may be asked to complete optional phone or video interviews to gain more insight into their experiences with and opinions on the chatbot. Approximately 15 to 20 participants will be sought for the interviews. The questions for these interviews will be developed based on the collective results from the quantitative and qualitative analysis described above.

Data Analysis

Quantitative data will be entered into SPSS version 26 (IBM Corp., Armonk, NY, USA) for statistical analysis. Comparisons between the treatment and control groups will be performed using four mixed analysis of variance (ANOVA) statistical tests, with experimental group and health condition as the between-subjects factors, time point as the within-subjects factor, and

mental health outcomes (i.e., scores on the Patient Health Questionnaire, Generalized Anxiety Disorder Scale, Perceived Stress Scale, Satisfaction with Life Scale) as the dependent variables. Significant interactions will be followed up with repeated measures ANOVAs (one within each experimental group) and dependent t-tests with Bonferroni adjustments, as needed.

Qualitative data will be analyzed using Braun and Clarke's (2006) six phases of thematic analysis: (1) familiarize oneself with the data; (2) generate initial codes; (3) search for themes; (4) review themes; (5) define and name themes; and (6) provide the report. This analysis will be performed on the qualitative data from the post-study questionnaire as well as the phone or video interviews. Qualitative data management will be performed with the assistance of NVivo version 12 (QSR International, Burlington, MA, USA).

Implications

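### Objective 1 is tested on four unranked scales, with no primary scale, no rule for a mixed result and no adjustment across scales

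*Combined protocol and SAP*

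**What the plan says.** The opening section gives objective 1 as "to determine whether a mental health chatbot can reduce or prevent negative mental health symptoms" in people with a chronic condition. Procedure introduces "four psychological assessments tools: measures of depression", then anxiety, stress and life satisfaction, without ranking them. All four are completed at the start, at two weeks and at four weeks.

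Data Analysis compares the arms by "four mixed analysis of variance (ANOVA) statistical tests, with experimental group and health condition as the between-subjects factors", with time point as the within-subjects factor. The dependent variables are "scores on the Patient Health Questionnaire, Generalized Anxiety Disorder Scale, Perceived Stress Scale, Satisfaction with Life Scale". It continues: "Significant interactions will be followed up with repeated measures ANOVAs (one within each experimental group) and dependent t-tests with Bonferroni adjustments, as needed".

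Sample says that "a total of 40 participants would be required for the quantitative portion of the study", on a moderate effect, power .80, alpha .05 and a correlation of .50 between repeated measures. The plan seeks 60, to strengthen the analysis. No outcome is named in the power statement, and .05 is not divided among outcomes.

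**The concern.** Objective 1 is worded as a single question, and the plan puts four tests to it. It does not say which scale decides, how many must be significant, or what one significant result out of four would mean. The follow-up sentence implies that the treatment effect is an interaction with time, but the plan never names the group-by-time term as the treatment test.

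The Bonferroni adjustment does not fill this gap. It comes into play within a scale, after that scale's interaction is significant, so it has no bearing on the chance that at least one of the four interactions is significant by luck.

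At stake is how the result is read. The Implications section draws several practical consequences from a positive finding. As the plan stands, one chance-positive scale could carry them.

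**Working it through.** **Inputs from the documents.** Four ANOVAs; 2 × 2 between-subjects cells (group by condition); m = 3 time points; alpha .05; power .80; correlation over time ρ = .50; N = 40 required and 60 sought.

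**Assumptions.** Moderate means f = .25. Cells are equal. Between-scale correlation r runs from 0 to .9, because the documents give none. The F test has no direction, so half of each .05 is counted as favouring the chatbot.

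**1. The plan's own figure.** For the interaction of time with the four cells:
- λ = f²·N·m/(1 − ρ) = .0625 × 40 × 3/.50 = 15
- df1 = (4 − 1)(3 − 1) = 6; df2 = (40 − 4) × 2 = 72
- power at .05 = .805, and 40 is the smallest N that reaches .80.

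So 40 is what one ANOVA needs at an unadjusted .05. The document does not say which G*Power option was used, but this one reproduces its figure.

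**2. Chance of at least one false positive, if any one scale may count.** With independent scales:
- either direction: 1 − .95⁴ = .185
- in the chatbot's favour: 1 − .975⁴ = .096.

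For correlated scales, the planned 2 × 2 × 3 ANOVA was simulated under no effect (N = 60, 15 per cell, group-by-time F on 2 and 112 df, 600,000 trials per value of r). In favour means significant, with the better baseline-to-week-4 change in the treatment arm.

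| r between scales | Either direction | In favour |
|---|---|---|
| 0 | .186 | .096 |
| .5 | .159 | .082 |
| .8 | .118 | .061 |
| .9 | .097 | .050 |
| one test alone | .05 | .025 |

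**3. If the follow-ups were also required.** Suppose benefit also needed a significant treatment-arm ANOVA and a baseline-to-week-4 improvement significant at .05/3. False benefit would then be .006 to .010 with no time trend, and .034 to .065 if both arms improved by 0.3 SD.

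**4. Holm across the four scales.** The strictest step is .05/4 = .0125. With independent scales the error in either direction is 1 − .9875⁴ = .049. Power uses the λ of step 1, with df2 = 2(N − 4):

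| Test, f = .25 | N | at .05 | at .0125 |
|---|---|---|---|
| group-by-time, 2 df | 60 | .991 | .966 |
| group-by-time, 2 df | 40 | .935 | .828 |
| four-cell, 6 df | 60 | .954 | .871 |
| four-cell, 6 df | 40 | .805 | .614 |

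On the 6-df basis, .80 power at .0125 needs 53 participants, or 56 with equal cells.

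**5. A smaller effect.** If the arms differ by 0, d/2 and d SD at the three times, each arm's interaction deviations are ∓d/4, 0 and ±d/4, so f² = d²/24. Then f = .25 means d = .25 × √24 = 1.22. At d = 0.8, λ = (.64/24) × 60 × 3/.50 = 9.6, and 2-df power at N = 60 is .787 at .05 and .598 at .0125.

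**The case against.** Four points can be made for the plan.

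- **Separate questions.** Depression, anxiety and stress could each be reported on their own terms, and each statement would keep its .05. This is a legitimate design, but the plan does not choose it.
- **The follow-ups act as a filter.** An omnibus F has no direction, so a claim of benefit needs a further look, and step 3 shows that a strict rule would lower false benefit a good deal. This stands as arithmetic. However, the plan calls for the follow-ups only as needed and does not make them a condition for success.
- **The scales are related.** Four self-report mental health scales are unlikely to be uncorrelated, so the upper figures are a ceiling. This stands.
- **Life satisfaction is arguably not a negative symptom.** With three independent scales the rates are 1 − .95³ = .143 in either direction and 1 − .975³ = .073 in favour. The figures are smaller, but the gap is the same.

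A reader might infer that the trial has a false-positive rate of .19, or that reading one significant scale as a chatbot effect always carries more than .05. The documents support neither. The first needs a counting rule that the plan does not state and a correlation of zero. The second fails for false benefit at r = .9 (.050) and in most of the range when follow-ups are required.

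**Conclusion.** The gap is plain on the text and needs no correlation assumption: there is no primary scale, no rule for a mixed result and no error control across the four scales. The Bonferroni wording does not supply one, and the sample size makes no allowance for four tests.

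The size is conditional. It rests on no true effect, one group-by-time test per scale at .05, and any one scale being allowed to count. On those terms the error in either direction lies between about .10 and .19 for r from .9 down to 0, and the error in the chatbot's favour between about .05 and .10. Both fall towards the single-test values as r nears 1.

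Each ANOVA also yields other terms involving group, so a reader might infer still higher rates. Those too would need a counting rule that the plan does not contain. The point is worth correcting, but it does not undermine the design.

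**What to change.** In Data Analysis:

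1. Name the group-by-time interaction as the treatment-effect test.
2. Name one scale as primary at two-sided .05, before data are seen.
3. Label the other three scales, and all other ANOVA terms including the three-way interaction, secondary or exploratory.
4. State that all four scales will be reported, and that a single significant non-primary scale will not be read as meeting objective 1.

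**Cost.** A few sentences. The primary scale loses no power; the plan gives up only confirmatory claims on the other three.

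**Alternative, if no scale can be ranked first.** Apply Holm to the four group-by-time tests at overall .05. This needs no choice of scale. At N = 60 and f = .25 the loss at the strictest step is modest. It is not small if recruitment ends near 40 and the 6-df basis applies (.805 to .614), or if the effect is smaller (.787 to .598 at 0.8 SD and N = 60, 2-df test).

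### The plan tests whether the arms differ over time but plans no treatment-minus-control estimate with a confidence interval; its only follow-up is within each arm

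*Combined protocol and SAP*

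**What the plan says.** The first objective, in the opening section, is "to determine whether a mental health chatbot can reduce or prevent negative mental health symptoms". Under Procedure, "Participants will be randomly assigned to either a treatment group or control group", and in both arms "participants will complete online materials via Qualtrics at the outset of the study, two weeks into the study, and four weeks into the study". The data therefore support a between-arm estimate at week 2 and at week 4.

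Under Data Analysis, "Comparisons between the treatment and control groups will be performed using four mixed analysis of variance (ANOVA) statistical tests", one per outcome, "with experimental group and health condition as the between-subjects factors, time point as the within-subjects factor". The only further step is: "Significant interactions will be followed up with repeated measures ANOVAs (one within each experimental group) and dependent t-tests with Bonferroni adjustments, as needed". Neither that section nor any other specifies a difference between arms at a time point, an effect size or a confidence interval. The section also does not say which interaction starts the follow-up.

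Under Sample, the power analysis gives 40 participants in total (moderate effect, power .80, alpha .05, correlation .50), and "a larger number of participants (N = 60) will be sought to strengthen the analysis".

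**The concern.** The group-by-time F test has 2 degrees of freedom. It says whether the two courses differ, but not by how much or with what uncertainty. The follow-up does not supply this, because a repeated-measures ANOVA or dependent t-test within one arm measures change from that arm's own baseline.

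Two things are at stake. If group-by-time is not significant, no planned result separates a chatbot with no effect from a trial too imprecise to show one. If it is significant, the planned follow-up describes each arm's change but does not estimate the difference between arms. It can also come up empty when each arm contributes part of the difference. The plan gives no rule for reading the within-arm results together.

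**Working it through.** **Inputs.** From the documents: two arms, two conditions, three time points, correlation .50, alpha .05, N = 40 (power analysis) and N = 60 (target). Assumed, because the documents do not give them: equal cells (15 each at N = 60), normal scores with SD 1, the same correlation between every pair of time points, a linear course unless stated, no dropout, and all effect sizes.

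**Step 1. Reproduce the plan's N.** Read 'moderate' as f = 0.25 (assumed) and use a within-between interaction with four cells and three times:
- λ = N × 3 × f² / (1 − ρ) = 40 × 3 × 0.0625 / 0.5 = 15
- df = (4 − 1)(3 − 1) = 6 and (40 − 4)(3 − 1) = 72
- power = 0.805 at N = 40 and 0.778 at N = 38

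So N = 40 is reproduced, but as a pooled 6-df interaction. Group-by-time in the planned model has 2 df, so the Sample section does not identify the test of the chatbot either.

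**Step 2. Put f = 0.25 in SD units.** Suppose it lies wholly on group-by-time and the week-4 difference is d. For a linear course f = d/√24, so d = 0.25 × √24 = 1.22 SD. If the full effect is present from week 2, f = d/√18, so d = 0.25 × √18 = 1.06 SD.

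**Step 3. How often is group-by-time non-significant at N = 60?** For a linear course λ = 60 × 3 × (d²/24) / 0.5 = 15d², with 2 and (60 − 4) × 2 = 112 df.

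| True week-4 difference | λ | Power | Non-significant |
|---|---|---|---|
| 0.5 SD | 3.75 | 38% | about 62% |
| 0.8 SD | 9.6 | 79% | about 21% |
| 1.22 SD (f = 0.25) | 22.5 | 99% | about 1% |

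For 1.06 SD present in full from week 2, λ is again 22.5 and the result is again about 1%. Simulation of the full 2 × 2 × 3 ANOVA (20,000 replicates per scenario) agrees.

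**Step 4. What the within-arm ANOVAs show after a significant group-by-time test.** Simulated at N = 60. The percentages are of trials with a significant group-by-time test.

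| Pattern | Difference | Treated significant | Control significant | Neither |
|---|---|---|---|---|
| Shared equally (treated improve, controls worsen) | 0.5 SD | 43% | 41% | 27% |
| Shared equally | 0.8 SD | 57% | 57% | 14% |
| Only treated improve | 0.5 SD | 92% | 7% | 6% |
| Only treated improve | 0.8 SD | 99.6% | 5% | 0.3% |
| Only controls worsen | 0.5 SD | 8% | 91% | 7% |
| Only controls worsen | 0.8 SD | 5% | 99.5% | 0.4% |

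As a share of all trials, 'neither' in the shared case is 0.38 × 0.27 = 10% at 0.5 SD and 0.79 × 0.14 = 11% at 0.8 SD.

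**Step 5. A misleading pattern with no chatbot effect.** If both arms improve by 0.4 to 0.5 SD, 'treated significant, control not' follows a significant group-by-time test in about 2% of all trials per outcome. After group-by-time or the three-way term it is about 3%.

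**Step 6. The estimate the plan could report.** Regress the week-4 score on arm, baseline and condition. The residual variance is 1 − 0.50² = 0.75.
- N = 60: 2.003 × √(0.75 × 2/30) = 0.448, about ±0.45 SD
- N = 40: 2.028 × √(0.75 × 2/20) = 0.555, about ±0.56 SD

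**The case against.** The strongest reply is that the plan already has a valid between-arm comparison. It names the mixed ANOVA as that comparison and uses within-arm tests only after a significant interaction. This stands. A reader might infer that the trial judges the chatbot by comparing significance within arms. The text does not say so, and step 5 shows that the misleading pattern is uncommon when follow-up depends on an interaction involving group and time.

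The follow-up is also not empty. It addresses direction and timing within each arm. When only one arm changes, it usually shows which one, including the 'prevent' case in objective 1 where only controls worsen. The 27% and 14% need the difference to be split equally between the arms.

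A reader might also make more of the unnamed trigger, since a condition-by-time interaction would qualify on a literal reading. In context the sentence most naturally means interactions involving group. Even read literally, the misleading pattern occurs in about 5% of trials. It reaches 11–12% or 19–20% only if diabetes and arthritis differ in course by an assumed 0.5 or 0.8 SD, and nothing in the documents supports such a difference. Naming the trigger is a minor clarification.

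Investigators may report means and intervals unprompted, but the plan does not commit them to it. None of these replies supplies the missing estimate.

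**Conclusion.** The point holds as a gap in estimation, not as a fault in the test. Group-by-time is sound, but the size and precision of the between-arm effect are not planned results under either outcome of that test. This should be fixed, because the scores needed are already collected in both arms.

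Its practical weight depends on the true effect. At 0.5 SD most trials of this size (about 62%) would end with a non-significant interaction and no planned interval to interpret it. At the effect implied by f = 0.25 only about 1% would. The absence of a planned estimate is read directly from the document. The percentages rest on the assumptions listed under the inputs, notably equal cells, a linear course and no dropout.

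**What to change.** Keep the four mixed ANOVAs and replace the follow-up sentence with:

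> The group-by-time interaction is the test of the chatbot for each outcome. Whatever its result, the treatment-minus-control difference at week 4, adjusted for baseline score and health condition, will be reported for each outcome with an unadjusted 95% CI, as the estimate of size and precision; the week-2 difference is secondary. No separate significance claim will be made from these contrasts, so no Bonferroni adjustment applies to them. If a CI and the group-by-time test disagree, both are reported and group-by-time remains the test. A significant group-by-condition-by-time interaction will be followed by the same between-group contrast within each condition, as exploratory. A condition-by-time interaction alone is not evidence on the chatbot. Within-group changes are descriptive only.

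The cost is a revised paragraph and a little more analysis in the same software, with no new data. The intervals will be wide, as step 6 shows, and within one condition (15 per arm) they are about ±0.65 SD. The unadjusted CI can exclude zero when group-by-time is not significant: about 24% of trials at 0.5 SD and 16% at 0.8 SD. The reverse occurs in about 3% and 1%. The rule on disagreement is there for these cases.
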